8.4. Baseline/Enrollment (Study Day 1)

Procedures/Assessments/Evaluations in this section will be completed after consent has been obtained, eligibility has been confirmed and the subject has been randomized. These do not need to be performed in the order listed below, but the administration of CCP must be the last procedure to be completed.

- 1- Demographics
- 2- Co-morbidities
- 3- Smoking status and pack-years for smokers
- 4- COVID-19 history (symptom onset, date of test, results of test)
- 5- Admission date
- 6- Oxygen saturation and PaO₂ (where available)
- 7- FiO2 and oxygen requirement (nasal prongs, oxygen masks, high-flow nasal cannula, noninvasive positive pressure ventilation)
- 8- Vital signs (temperature, pulse, respiratory rate, height, weight, and blood pressure)
- 9- Lab values
- 10- Patient-reported outcome instrument EQI-5D-5L 49
- 11- AEs since screening (if screening was not completed on the same day)
- 12- Concomitant medication review (if screening was not completed on the same day)
- 13- COVID-19 concomitant treatments including co-enrolment in another clinical trial
- 14- Administration of investigational product (according to study arm)

8.5. Collection of daily hospital data (Study Day 2 until discharge, death or Day 30 post randomization).

The following data and procedures will be collected daily.

- 1- Oxygen saturation and FiO₂
- 2- Mechanical ventilation requirement (via endotracheal tube or tracheostomy tube)
- 3- Admission to ICU
- 4- ECMO requirement
- 5- Renal replacement therapy requirement
- 6- Myocarditis
- 7- COVID-19 concomitant treatments
- 8- Blood product and blood transfusion information
- 9- AEs
- 10- Concomitant medication review
- 11- Chest x-ray and CT chest results
- 12- Discharge status (home, transfer to another facility, palliative discharge) collected from the hospital chart

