4.2. Participant recruitment

Only hospitalized COVID-19 patients are eligible so recruitment efforts will be focused on identifying consecutive patients admitted to hospital with acute COVID-19 infection. No other external recruitment efforts are planned. At each participating hospital, a process for immediately identifying admitted patients with COVID-19 will be established. The mechanism of alerting the research assistants (RA) will be determined by local site principal investigator.

Patients who are confirmed to have COVID-19 infection and are admitted to hospital will be assessed for eligibility. Consent may be obtained verbally, given the infection control precautions

in place for these participants, as permitted by local research ethics committees. The RA (or a bedside physician if deemed acceptable by local research ethics boards [REB]) will obtain consent from the patient or legally authorized representative (LAR) by phone or videoconference. After consent is obtained, the RA will confirm eligibility remotely through a review of the electronic medical record and discussion with the bedside physician/nurse. Informed consent will be obtained remotely and may use a variety of visual aids (video brochure, a visual decision board). Documented written consent will be obtained from the patient or LAR as soon as possible as required by local REBs. At the time of assessing eligibility the RA will confirm with the site storing CCP that an ABO-compatible CCP plasma unit is available (for certain sites, group A plasma with low-titer anti-B (≤1:50) is allowed to be transfused to group B or AB patients). If 500 mL of CCP is available and eligibility criteria are met, the RA will randomize the patient. The RA will notify the blood bank of the allocation and a marker will be placed in the Laboratory Information System and the patient chart indicating that the patient is enrolled in the CONCOR-1 trial. For patients randomized to CCP, the RA will notify the bedside physician to order the study product. The CCP will be thawed in the blood bank, issued, and infused by the bedside nurse within 24 hours of randomization.

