4.6. Blinding and Unblinding Procedures

This is an open-label trial. The decision to perform the trial unblinded was based on the following reasons: (1) to allow for participation of academic and non-academic hospital sites where masking procedures are not possible given the required short implementation timelines; (2) to avoid exposing patients to the risks of a standard plasma arm as the placebo has no anticipated benefit; (3) to avoid the need to create an inert placebo (e.g. coloured saline) including the need to mask, which would cause significant disruption of workflow and additional use of PPE during the pandemic.

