8.3. Collection of daily hospital data

Baseline data will be collected on Day 1 (see Section 8.5).

During the index hospital admission, daily data will be collected until discharge or Day 30 from randomization, whichever comes first. For enrolled patients who are still in hospital beyond Day 30, the date of discharge or death will be recorded up until Day 90 at which point data collection will be censored. This information will be obtained by reviewing the medical chart, by telephone follow-up or, if feasible through, provincial/state or national databases.

If the patient has routine blood drawn for laboratory testing pre-randomization and between 24 hours and 5 days (sample closest to 48 hours will be selected in preference) post-randomization, the discard plasma/serum from that sample will be retrieved, aliquoted and frozen for future testing. Alternatively, an extra tube can be added to the routine blood draw for research.

A Schedule of Assessment Events is available below for reference.

Schedule of Assessment Events

			Follow up		
Visit	Screening	Baseline (D1)	D2 - D30 ⁽¹⁾ (or until discharge)	D30 ⁽²⁾ (if patients discharged)	D90
Time Window (days)				+/- 3	+/- 7 days
Informed Consent/Assent	Х				
Verify Eligibility Criteria	X				
Randomization		Х			
CCP Administration (3)		Х			
Demographics		Х			
Co-morbidities		Х			
COVID-19 History ⁽⁴⁾		Х			
Height and Weight		Х			
Vital Signs		Х			
SpO ₂		Х	Х		
FiO ₂		Х	X		
COVID treatments		Х	Х	Х	
Hospitalization Daily Assessment (5)		Х	X		
Results of blood tests (done as per		Х	X ⁽⁶⁾		
clinical need)					
EQ-5D-5L ⁽⁷⁾		Х		Х	
Vital Status (dead/ alive)			Х	Х	X
Adverse Event Review		Х	Х	Х	
Discharge status (8)				Х	
Mechanical Ventilation since discharge				Х	
Viral load, cytokines and anti-CoV-2 titers ⁽⁹⁾		Χ	Х		

⁽¹⁾ Only collected if still hospitalized

⁽²⁾ Phone call if subject is already discharged from the hospital

⁽³⁾ Only for subject randomized to the convalescent plasma treatment

⁽⁴⁾ Includes date of first symptoms; description of symptoms, and date of diagnostic test

⁽⁵⁾ Mechanical ventilation, ECMO, renal replacement therapy or myocarditis

⁽⁶⁾ Daily from Day 1-7, then Day 14 +/- 3 days

⁽⁷⁾ EQ-5D-5L to be collected on Day 1 after consent and prior to CCP administration and on Day 30 regardless of hospitalization status

⁽⁸⁾ Discharge or hospital status (admitted, home, local hospital, longterm care facility)

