8.6. Laboratory Test Results

The following laboratory testing results will be recorded only if ordered by the bedside team at baseline (most recent results from day of randomization or previous 2 days), daily until Day 7, and at Day 14 (+/- 3 days).

- 1. CBC
- 2. INR, PT, aPTT, Fibrinogen, D-dimer
- 3. ALT, ALP, Bilirubin (total)
- 4. Albumin
- 5. Creatinine
- 6. LD
- 7. CK, C-Reactive Protein, Total Protein
- 8. Blood gas results (PaO₂, PaCO₂)
- 9. Ferritin
- 10. Total CO2
- 11. Troponin I HS
- 12. Lactate

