4.3.11. Patient-reported outcomes (PROs)

The original responses from each patient will be converted into a single utility index score anchored at 0 for dead and 1 for full health using the scoring algorithm based on Canadian society preferences. Utility changes from baseline to Day 30 were estimated by analysis of covariance adjusting for baseline utilities and compared between the two arms.

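### Baseline EQ-5D-5L, oxygen requirement and co-enrolment status are scheduled after open-label randomization, so one ANCOVA covariate and two subgroup factors can reflect knowledge of the arm

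*Protocol*

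**What the plan says.** Protocol 8.4, the baseline section for Study Day 1, opens: "Procedures/Assessments/Evaluations in this section will be completed after consent has been obtained, eligibility has been confirmed and the subject has been randomized". The order of items is free, except that "the administration of CCP must be the last procedure to be completed". The list includes oxygen saturation (item 6), FiO2 and oxygen requirement (item 7), the EQ-5D-5L (item 10) and co-enrolment in another trial (within item 13).

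Other places that bear on this:

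- **Protocol 8.3, schedule footnote 7:** "EQ-5D-5L to be collected on Day 1 after consent and prior to CCP administration". This permits collection before randomization but does not require it, and 8.4 places it after.
- **Protocol 4.6:** "This is an open-label trial". Under Protocol 4.2 plasma is to be "infused by the bedside nurse within 24 hours of randomization".
- **SAP 2.1:** Day 1 is the date of randomization.
- **SAP 4.3.11:** "Utility changes from baseline to Day 30 were estimated by analysis of covariance adjusting for baseline utilities and compared between the two arms". Protocol 12.4.2 plans a comparison of change from baseline and does not mention adjustment.
- **Protocol 12.4.4 and SAP 4.4:** oxygen status at baseline (cut at 2 L) and enrolment in other therapeutic trials are subgroup factors. The co-enrolment factor carries no time point.

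**The concern.** A baseline covariate or subgroup factor is safe in a randomized comparison because allocation cannot have influenced it. That guarantee is lost once the value is taken after an unblinded allocation.

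The EQ-5D-5L is the most exposed item. It is self-reported, and one of its five dimensions is anxiety/depression (SAP 2.2.11). A patient who has just learned whether plasma will be given may answer differently. If so, the covariate differs between arms for a reason other than chance, and ANCOVA adjusts for a difference it should not remove.

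Co-enrolment is allowed (Protocol 4.1.2), and knowing the arm can affect whether a patient enters another trial. Oxygen requirement is more objective, but its recorded value can include some hours of clinical course after randomization, and staff know the arm.

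At stake are one secondary outcome and two subgroup factors for the primary outcome.

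**Working it through.** **1. What can and cannot be reproduced.** The plan gives no figure on this point. Its only related design figure is the sample size: 30% against 22.5%, 2:1, two-sided 0.05. With pooled variance this gives 400 controls and 1200 in total, with power 0.801, so the stated 1200 is reproduced. The timing of baseline does not alter it. The primary analysis (SAP 4.2) is an unadjusted Wald test and uses no baseline value.

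**2. Timing, read across the sections.** Randomization comes first, then the 8.4 items in any order, then plasma. The plasma-last rule keeps the effect of plasma itself out of baseline. Day 1 caps baseline in both arms at the end of the calendar day of randomization. What remains is knowledge of the arm, plus at most the rest of that day's clinical course.

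**3. ANCOVA bias.** Let the recorded baseline be higher by *d* in the CCP arm than in controls because the arm is known. Let *b* be the within-arm slope of Day 30 utility on baseline. If the shift does not carry through to Day 30 and there is no true effect:

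bias in (CCP − control) = −*b* × *d*

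SE ≈ SD × √(1 − *b*²) × √(1/n₁ + 1/n₀)

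None of the following inputs is in the documents; all are assumptions: *d* = 0.02 to 0.05, *b* = 0.3 to 0.5, SD = 0.25, completers 600 and 300, so √(1/600 + 1/300) = 0.0707.

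| *b* | *d* | bias | SE | bias/SE |
|---|---|---|---|---|
| 0.3 | 0.02 | −0.006 | 0.0169 | 0.36 |
| 0.3 | 0.05 | −0.015 | 0.0169 | 0.89 |
| 0.5 | 0.02 | −0.010 | 0.0153 | 0.65 |
| 0.5 | 0.05 | −0.025 | 0.0153 | 1.63 |

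A simulation (1000 runs per setting, SD 0.25, 800 against 400, no true effect) agrees. At *b* = 0.3 and *d* = 0.02 the mean bias was −0.0057 and the nominal 5% test rejected in 6.6% of runs. At *b* = 0.5 and *d* = 0.05 these were −0.0245 and 45.5%. An unadjusted change score, as Protocol 12.4.2 could be read, carries the full shift, −0.02 to −0.05. The bias does not shrink with more patients.

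**4. Oxygen subgroup, as an illustration.** Assume half the patients in each stratum, risks of 15% (≤2 L) and 45% (>2 L), and no treatment effect. A fraction *m* of control patients truly at ≤2 L, with risk 30%, is recorded as >2 L. None of this is in the documents.

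- *m* = 2%: control risk at ≤2 L is (0.075 − 0.003)/0.49 = 0.1469, so RR = 0.15/0.1469 = 1.02. Above 2 L it is (0.225 + 0.003)/0.51 = 0.4471, so RR = 1.01.
- *m* = 10%: (0.075 − 0.015)/0.45 = 0.1333, so RR = 1.13. Above 2 L, (0.225 + 0.015)/0.55 = 0.4364, so RR = 1.03.

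This needs recording that differs by arm. Clinical course alone, observed over the same hours in both arms, would not produce it.

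**The case against.** The best defence is that the exposure is narrow and its size invented. Footnote 7 lets a site take the EQ-5D-5L before randomization. Protocol 4.2 describes telling the blood bank and the bedside physician of the allocation, and does not say when the patient learns it. Only one of five EQ-5D dimensions is an obvious route. No mechanism is shown by which allocation changes oxygen flow before plasma. All of this stands as a limit on size. It does not remove the problem, because 8.4 directs collection after randomization and nothing keeps the patient unaware.

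A reader might also infer several stronger things that the documents do not support:

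- **That every baseline value follows randomization.** Laboratory results may be the "most recent results from day of randomization or previous 2 days" (Protocol 8.6). The research sample uses pre-randomization blood where available (8.3), and the viral-load sample may be up to 48 hours earlier (SAP 4.6.2). Age group is a stratum (Protocol 4.3). Demographics, comorbidity and smoking history do not change in hours.
- **That controls have no time limit, or that the arms are measured at different times.** Day 1 applies to both. The 24 hours is the infusion window, not a baseline window.
- **That laboratory results drawn after plasma count as baseline.** Laboratory values are item 9 of the 8.4 list, and plasma comes last. No planned analysis uses them as a covariate or subgroup.
- **That the QALY difference is biased the other way.** That needs an area-under-the-curve calculation from baseline utility. SAP 4.3.12 on cost per QALY says only that the EQ-5D-5L is used. Under such a method the shift would add *d*/2 × 30/365, or 0.0008 to 0.0021 QALY, but this is conditional on a method not stated.

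**Conclusion.** The point holds for three items: the EQ-5D-5L, oxygen requirement and co-enrolment status. The written rule takes them after open-label randomization, and each feeds a planned analysis that assumes a value untouched by allocation. The consequence is possible bias in the adjusted utility comparison and in two subgroup analyses. The primary test and the sample size are unaffected.

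The size cannot be established from the documents. The range of 0.006 to 0.025 in utility, about 0.4 to 1.6 standard errors, rests wholly on the assumed shift, slope, SD and completer numbers. Its direction, against CCP, rests on the assumption that controls report worse utility after disclosure. These figures show sensitivity; they are not evidence that a shift occurred. The change is worth making because it is cheap and the SAP has no check that would reveal such a shift.

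**What to change.** - **Protocol 8.4 and footnote 7:** require the EQ-5D-5L after consent and before the allocation is revealed.
- **Protocol 8.4 and the SAP:** define baseline oxygen requirement, SpO2/FiO2 and co-enrolment status as the last value before the randomization time stamp, and flag any later value. The flag also covers patients already enrolled under the present wording.
- **SAP 4.4 and Protocol 12.4.4:** state that the co-enrolment subgroup uses status at that time point.
- **SAP section on cost per QALY:** state whether and how baseline utility enters the calculation.
- **Protocol 8.3:** correct the pointer for baseline data, which names 8.5 although the list is in 8.4.

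The cost is wording, a reordered Day 1 checklist, a few minutes before randomization, and a questionnaire completed by the few consented patients who are not then randomized. Consent and eligibility review already precede randomization (Protocol 4.2), and receipt of supplemental oxygen is an inclusion criterion, so much of the contact already takes place at that point.

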8.6. Laboratory Test Results

The following laboratory testing results will be recorded only if ordered by the bedside team at baseline (most recent results from day of randomization or previous 2 days), daily until Day 7, and at Day 14 (+/- 3 days).

- 1. CBC
- 2. INR, PT, aPTT, Fibrinogen, D-dimer
- 3. ALT, ALP, Bilirubin (total)
- 4. Albumin
- 5. Creatinine
- 6. LD
- 7. CK, C-Reactive Protein, Total Protein
- 8. Blood gas results (PaO₂, PaCO₂)
- 9. Ferritin
- 10. Total CO2
- 11. Troponin I HS
- 12. Lactate

8.7. Discharge

- 1. Hospital / Discharge status (home/local hospital/longterm care facility)
- 2. Oxygen requirement
- 3. Need for mechanical ventilation
- 4. AEs

8.8. **Day 30**

- 1. Vital status (dead or alive)
- 2. Requirement for mechanical ventilation since discharge
- 3. Oxygen requirement
- 4. Hospital status (home/local hospital/longterm care facility)
- 5. Readmission to hospital (if discharged home/longterm care facility)
- 6. EQ-5D-5L
- 7. AEs

8.9. Day 90 follow-up

Occurrence and date of hospital death or discharge (for participants still hospitalized at Day 30 only).

8.10. Protocol Deviations

A protocol deviation is any noncompliance with the clinical trial protocol, any process that is noted in the protocol and refers to details in the protocol-specific operations manual or Good Clinical Practice (GCP) requirements or any critical study procedures with specific instructions in ancillary documents referenced in the protocol such as a protocol-specific operations manual.

It is the responsibility of the investigator to ensure that only investigative procedures, as outlined in this protocol are performed on study participants; the occurrence of deviations from the protocol or SOPs are limited; and compliance with the regulations is maintained. Planned deviations from the protocol must not be implemented without prior agreement from the sponsor and approval from the local REB/ethics committee, as required, unless to eliminate an immediate hazard to a participant.

Planned or unplanned deviations may occur on the part of the participant, the investigator, or study research team. In resolution to a deviation, corrective/preventative actions are to be developed and implemented in a timely manner. Protocol deviations will be documented and reported as required and assessed where necessary during analysis. All individual protocol deviations will be addressed in subject study records.

It is the responsibility of the site PI and personnel to use continuous vigilance to identify and report deviations within five working days of identification of the protocol deviation, or within five working days of the scheduled protocol-required activity. All deviations must be promptly reported per the protocol deviation reporting procedures. Protocol deviations must be sent to the local REB per their guidelines. The site PI and personnel are responsible for knowing and adhering to their REB requirements. A completed copy of the Protocol Deviation Form must be maintained in the Essential Documents, as well as in the subject's chart if the deviation is subject specific.

9. SAFETY VARIABLES

9.1. Adverse Event

An AE is any untoward medical occurrence that occurs in a patient or clinical investigation subject administered a pharmaceutical product, and which does not necessarily have a causal relationship with the treatment assignment. An AE can therefore be any unfavorable and unintended sign (including abnormal laboratory finding), symptom, or disease temporally associated with the use of an investigational product, whether or not considered related to the product.

Because this is a trial focusing on a critically ill population where serious adverse events and death are expected to occur frequently, AE reporting will follow recommendations set out for trials in this population by Cook and colleagues⁵⁰. During this trial, investigators will need to document all AEs that are definitely or probably related to the intervention (defined in 9.4.1), and events that are grade 3 or higher for all other AEs.

These will be documented on the paper CRF and in the electronic CRF (e-CRF) with the maintenance of all source documentation in the patient research file. Concomitant illnesses, which existed before entry into the study, will not be considered AEs unless they unexpectedly worsen during the treatment period. AEs must be documented regardless of the source of identification (for example physical examination, laboratory assessment, reported by subject).

9.2. Serious Adverse Event

A SAE is generally defined as any untoward medical occurrence that at any dose:

- 1. Results in death;
- 2. Is life-threatening; this means that the subject is at risk of death at the time of the event; it does not mean that the event hypothetically might have caused death if it was more severe;
- 3. Requires hospitalization (overnight or longer) or prolongation of existing hospitalization or invasive procedure;
- 4. Results in persistent or significant disability or incapacity;
- 5. Results in congenital anomaly or birth defect;
- 6. Is not be immediately life-threatening or result in death or hospitalization but may jeopardize the subject or require intervention to prevent one of the above outcomes.

Events associated with hospitalization for the following will **not** be considered as an SAE:

- 1. Evaluation or treatment of a pre-existing and non-exacerbating condition as long as the condition is associated with the hospitalization (e.g. hospitalization for investigation of a benign disorder);
- 2. Existed prior to the subject's entry into the study and has been recorded in the subject's disease/medical history as documented in the e-CRF;

- 3. Has not worsened in severity or frequency during the subject's exposure to investigational product;
- 4. Has not required a change in treatment management during the subject's exposure to the investigational product;
- 5. Elective or pre-planned treatment of a pre-existing and non-exacerbating condition.

In the specific context of a clinical trial focussing on a critically ill population, the definition of SAE also excludes:

- a. AEs that are part of the natural history of the primary disease process or expected complications of critical illness.
- b. AEs that are already captured as study outcomes.

Medical and scientific judgment should be exercised in deciding whether an AEs is serious and whether expedited reporting is appropriate. Caution must also be exercised by the investigator when attributing death or prolonged hospitalization to a specific AE. All-cause mortality and hospitalization stay will be captured as study outcomes.

9.3. Severity of Adverse Events

The severity of each AE must be assessed by the Investigator and graded based on CTCAE v4.0. A clinical AE NOT identified elsewhere in the grading table will be graded using one of the following categories:

- 1. **Mild**: Mild symptoms causing no or minimal interference with usual social & functional activities with intervention not indicated
- 2. **Moderate**: Moderate symptoms causing greater than minimal interference with usual social & functional activities with intervention indicated
- 3. **Severe**: Severe symptoms causing inability to perform usual social and functional activities with intervention or hospitalization indicated
- 4. **Life-threatening:** Potentially life-threatening symptoms causing inability to perform basic self-care functions with intervention indicated to prevent permanent impairment, persistent disability, or death.
- 5. **Death:** The AE resulted in the subject's death.

